#### **5.4 Specific Study Sessions**

##### **5.41 Signing the informed consent form**

Patients should sign an informed consent form before enrollment, and the investigator should explain the content and significance of the study to patients and their families, and inform them of their rights and obligations. The informed consent should be signed by the patient and his or her legal representative.

##### **5.42 Prior to randomization**

The following data must be collected for all subjects prior to randomization and registration:

Confirmation that all enrolled patients meet the inclusion/exclusion criteria.

Demographic information and past history.

Vital signs.

Neurological function tests (NIHSS score, mRS score).

Routine blood count, blood biochemistry and coagulation.

Neuroimaging: MRI/CT to assess for intracranial hemorrhage; MRA/CTA/DSA to confirm that the occlusion occurred in a large vessel of the anterior circulation, such as the internal carotid artery (ICA) or the M1 segment of the middle cerebral artery.

**Determination of time points:** For consistency and clarity, a time standard was established for this study, namely time 0 "t = 0" defined as the time of randomization; that is, after CT exclusion of intracranial hemorrhage and suspicion of acute anterior great vessel occlusion (ICA or MCA-M1) based on clinical signs and symptoms, all subsequent time points (e.g., 24 hours, first day of the week, and second day of the week) were determined. All subsequent time points (e.g., 24 hours, days 5-7, 30, and 90) were used as a

reference for randomization time (t=0). Time recording format: X day, X month, X month, X hour, X minute.

### **5.43 Endovascular Treatment Specifications**

Endovascular therapy includes mechanical embolization and balloon dilation or stenting. Thrombectomy allows the use of CFDA-approved thrombectomy devices such as stent-like devices and aspiration systems. For patients with underlying atherosclerotic stenosis after embolization, balloon dilation may be used alone, and stenting may be performed if necessary. For occluded vessels, no more than 5 thrombectomy attempts should be performed. Remedial measures after failed thrombectomy are permitted by pharmacologic arterial thrombolysis or intravenous infusion of antiplatelet agents, such as urokinase or rtPA arterial thrombolysis; rtPA is generally 1/3 of intravenous thrombolysis and can be administered intracatheterally, usually at a rate of 1 mg/min. urokinase is usually administered at a total dose of no more than 600,000 u at a rate of 1 to 20,000 U/min. Remedial therapy with balloon angioplasty or stenting is allowed. Failure to achieve a reperfusion grade of mTICI2b after remedial therapy is considered a failure of thrombus retrieval, and the case is considered a violation of the enrollment protocol, and the data can only be analyzed by mITT and cannot be included in the protocol compliance data set for PP analysis. In the case of re-occlusion at 24 hours after the procedure, it was also considered a recanalization failure and a violation of the enrollment protocol, and the data were analyzed only by mITT and not by PP.

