### 5.33 Study Implementation Process

Patient enrollment methods:

- A) Emergency greenway triage based on signs and symptoms and NCCT: In this study, a team of emergency department neurologists screened patients for possible large vessel occlusion at 6-24 hours of onset based on head CT scan and NIHSS score  $\geq 6$  and RACE score  $\geq 5$  as proposed subjects.
- B) Clearly diagnosed acute large vessel occlusion (ELVO)

Patients who have performed one of the MRI plain or perfusion examinations but do not meet the inclusion criteria for the DAWN or DEFUSE3 studies may be considered for inclusion. After enrollment, the appropriate imaging modality was selected according to the group as the basis for whether or not to perform interventional treatment.

Screening may be included in cases where either MRI or perfusion imaging is available at the time of the stroke specialist's evaluation of the patient, but the patient or authorized delegated family member is temporarily unable to decide whether to undergo the procedure, or under special irresistible conditions such as occupancy of the interventional suite.

Patients who met the entry criteria were then randomized 1:1 by the arriving stroke specialist into two groups 1 and 2 as follows, with the order of randomization being the responsibility of an independent investigator.

1. The MRI group performed DWI, FLAIRE, T1, T2 and MRA sequences.
2. The Control group underwent MRA or CTA, perfusion sequences, and F-stroke software (Brain Seal Smart Technology).

After randomization, the attending interventionalist decided the treatment based on the history and imaging data of the respective group. All patients were treated with the standard embolization procedure and or the optimal drug therapy. The primary outcome was the overall distribution of **MITT** patients' modified Rankin Scale scores at 90 days postoperatively in both groups, as assessed by the corrected co-ratio. Multiple secondary outcomes, including death, symptomatic intracranial hemorrhage, and

ischemic regional reperfusion, and safety outcomes were also assessed for the included study population.

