### **5.37 Outcomes**

The primary outcome was the modified Rankin Scale score (mRS 90d) of a randomized group of modified intention-to-treat (mITT) patients (defined as patients with acute macrovascular occlusions treated optimally with endovascular or pharmacologic therapy) at 90 days (with an assessment time window of  $\pm 14$  days) and analyzed for noninferiority. If the primary analysis indicated possible superiority, superiority was tested as a secondary objective. Data were collected by structured interviews (telephone interviews) with patients using a standardized form by trained physicians who were unaware of the subgroup results. A standardized written report of each interview was presented to two members of the outcome committee, who confirmed the scores and reached agreement.

The secondary outcomes were as follows:

Proportion of patients in each group receiving interventions Good prognosis for patients receiving interventions

- 1) Patient death within 90 days.
- 2) Successful reperfusion after embolization, defined as an extended Thrombolysis in Cerebral Infarction (eTICI) score of 2b, 2c or 3 at the time of the first intracranial angiogram.
- 3) Percentage of patients revascularized 24 to 72 hours after surgery (as determined by CTA).
- 4) NIHSS scores at 24 hours and 5 to 7 days postoperatively (or at discharge).
- 5) Final infarct volume (calculated by CBV or DWI) at 24 hours and 5 to 7 days postoperatively (or at discharge).
- 6) Comparison of modified Rankin scores at 90 days (0 or 1 vs. 2-6; 0-2 vs. 3-6; 0-3 vs. 4-6; 0-4 vs. 5 or 6; and 0-5 vs 6).
- 7) Quality of life assessment at 90 days: European Five Dimensions and Five Levels Scale (EQ-5D-5L) scores (range, -0.39 [worst] to 1.00 [best]); Barthel

Index scores at 90 days (range, 0 [severe disability] to 100 [no disability]).

Safety outcomes: included all hemorrhage and symptomatic intracranial hemorrhage (Judged by the Heidelberg Classification of Hemorrhage); intraoperative arterial puncture site pseudoaneurysm and inguinal hematoma, cerebral infarction in an additional vascular area at 5 to 7 days, and death within 90 days. The timing of clinical evaluation included at baseline, 24 hours after randomization, 5 to 7 days, or at discharge, whichever occurred first, and 90 days (with an assessment time window of  $\pm 14$  days).

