### **Termination of endovascular therapy**

- 1)Neurological deterioration suspected to be caused by intracranial hemorrhage;
- 2)Puncture time from the groin was up to 2 hours.
- 3)Spontaneous recanalization of the vessel.
- 4)The same site was embolized up to 5 times.For the procedure, the time of revascularization should be noted in detail;
- 5)the time from imaging to revascularization, the time from onset to revascularization, and the time from admission to revascularization should be calculated and used as baseline information for comparison between the 2 groups.

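### Section 5.43 counts failed reperfusion and 24-hour re-occlusion as violations and drops them from the PP set, so a PP comparison can be biased and would not measure compliance (minor; primary mITT analysis unaffected)

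*Protocol*

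**What the plan says.** Section 5.43 describes two events in patients who undergo the procedure. The first is failure to reach mTICI 2b after remedial therapy. The protocol calls this a violation of the enrolment protocol, and the "data can only be analyzed by mITT and cannot be included in the protocol compliance data set for PP analysis". The second is re-occlusion at 24 hours, of which 5.43 says "it was also considered a recanalization failure and a violation of the enrollment protocol", with the same consequence: kept in mITT, left out of PP.

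Other sections bear on this rule:
- Section 5.42 lists, among what is collected before randomisation, "Confirmation that all enrolled patients meet the inclusion/exclusion criteria". It sets time zero at randomisation.
- Section 5.43 also limits the procedure: "no more than 5 thrombectomy attempts should be performed". The list under Termination of endovascular therapy includes "Puncture time from the groin was up to 2 hours" and "The same site was embolized up to 5 times".
- Section 5.33 says that after randomisation "the attending interventionalist decided the treatment based on the history and imaging data of the respective group". Section 5.35 gives the two arms different imaging criteria for operating.
- Section 5.37 has secondary outcomes for successful reperfusion ("defined as an extended Thrombolysis in Cerebral Infarction (eTICI) score of 2b, 2c or 3 at the time of the first intracranial angiogram"), for revascularisation on CTA at 24 to 72 hours, and for the share of each group that receives an intervention.
- Section 5.34 places the primary analysis, a cumulative ordinal logistic regression of 90-day mRS, in the mITT population.

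PP is named only in 5.43.

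**The concern.** A per-protocol set is meant to show what happens among patients who were eligible and were handled as planned. The rule in 5.43 selects instead on how well treatment worked. Failed reperfusion and re-occlusion may plausibly be linked both to allocation, because the imaging arm informs who is operated on, and to the 90-day mRS. Dropping patients on such a result breaks the randomised comparison.

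Two things are at stake. The PP estimate can differ from the mITT estimate for reasons unrelated to adherence. And a reader who compares PP with mITT to judge robustness to non-compliance would learn little, because the PP set does not measure compliance.

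**Working it through.** **Step 1. Are the two events breaches of the protocol?** Setting the sections side by side:
- *Timing.* Eligibility is confirmed before randomisation (5.42). Both events follow the procedure, which comes after randomisation. Neither is an enrolment matter.
- *Conduct.* A team that stops at the attempt limit or the time limit without reaching mTICI 2b has done what the protocol asks, yet 5.43 labels the case a violation. Re-occlusion at 24 hours is likewise not, in itself, something done contrary to the plan.
- *Reach.* Patients on drug therapy alone cannot meet either criterion, so only operated patients can be removed. The share operated may differ by arm, and 5.37 treats it as an outcome.

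**Step 2. Size of a possible bias.** There is no figure in the protocol to reproduce; it gives no EVT rate, failure rate or mRS distribution. Everything below is an assumption except the total of 214 (Size of sample), the 1:1 allocation (5.1) and the model type (5.34).

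Assumed mRS 0 to 6 distributions (%), the same in both arms:
- S, EVT without failure: 14/20/20/16/14/6/10
- F, EVT with failure: 2/4/9/13/22/18/32
- M, drug therapy alone: 5/9/14/17/24/12/19

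With e the share given EVT and f the share of those who fail:
- all patients: e[(1−f)S + fF] + (1−e)M
- failures removed: [e(1−f)S + (1−e)M] / (1 − ef)

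A proportional-odds model is fitted by maximum likelihood to each pair of mixtures, with arms weighted by the share kept. An OR below 1 means the MRI arm does worse.

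| EVT, MRI v control | Failure, MRI v control | OR, all patients | OR, failures removed |
|---|---|---|---|
| 70% v 70% | 20% v 20% | 1.00 | 1.00 |
| 70% v 70% | 20% v 15% | 0.944 | 0.987 |
| 70% v 70% | 30% v 15% | 0.841 | 0.957 |
| 70% v 70% | 15% v 30% | 1.189 | 1.045 |
| 75% v 65% | 20% v 20% | 1.067 | 1.114 |
| 75% v 65% | 16% v 20% | 1.121 | 1.125 |
| 75% v 65% | 30% v 20% | 0.943 | 1.083 |

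*Check of the third row on mRS 0–2.* The assumed rates are 54% (S), 15% (F) and 28% (M).
- All patients, MRI: 0.7 × (0.7 × 54 + 0.3 × 15) + 0.3 × 28 = 38.0%.
- All patients, control: 0.7 × (0.85 × 54 + 0.15 × 15) + 0.3 × 28 = 42.1%. Difference −4.1 points.
- Failures removed, MRI: (0.7 × 0.7 × 54 + 8.4) / 0.79 = 44.1%.
- Failures removed, control: (0.7 × 0.85 × 54 + 8.4) / 0.895 = 45.3%. Difference −1.2 points.

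Patients removed in that row: 107 × 0.70 × 0.30 = 22.5 and 107 × 0.70 × 0.15 = 11.2. These are upper bounds, since they assume that every randomised patient is in the set.

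*Outcomes of failed cases differing by arm.* With EVT 70% and failure 20% in both arms, shifting the failed MRI-arm cases by an OR of 0.6 gives 0.949 → 1.000, and by an OR of 1.67 gives 1.061 → 1.000. Equal rates alone therefore do not guarantee an unbiased comparison.

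**Step 3. Scale against sampling error.** With 107 per arm, EVT 70% and failure 20%, the variance of the log OR is about 12 / [214 × (1 − Σp³)]. Here Σp³ = 0.0233, so the SE is √(12 / 209.0) = 0.240. The 95% CI factor is exp(1.96 × 0.240) = 1.60 either way.

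**The case against.** The strongest reply is that nothing in this document depends on PP. The primary analysis is in mITT, 5.43 expressly keeps these patients there, and the SAP, which is not shown, would commonly define the PP set and its use. That stands, and it caps the severity. It does not remove the point, because 5.43 fixes the exclusion in so many words, and an SAP with a conduct-based PP set would contradict it.

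The size is assumed throughout. With equal rates and equal outcomes by treatment class the bias is nil. With gaps of at most 5 points in both rates (EVT 60–80%, failure 10–30%) the shift is at most a factor of 1.085, small beside 1.6. This also stands.

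The word enrolment may be loose translation, and 5.42 is a list of baseline data, not a definition of a violation. True, but the PP exclusion is unambiguous whatever the label.

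A reader might infer three stronger points that the documents do not support:
- *That the non-inferiority conclusion is compromised.* The protocol gives PP no part in that decision.
- *That the rule favours the MRI arm or always pulls towards no difference.* The table shows movement in both directions, away from 1 as well as towards it, and near-cancellation in one row.
- *That the protocol excludes patients on its own secondary outcomes.* The measures in 5.37 are related, but they differ in scale or timing (eTICI at the first intracranial angiogram; CTA at 24 to 72 hours).

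**Conclusion.** The concern holds as a minor one. Section 5.43 classes two post-randomisation treatment results as violations and excludes them from PP, although they can occur with full compliance. A PP comparison built on this rule can be biased in either direction when EVT rates, failure rates or the outcomes of failed cases differ by arm, and it would not measure protocol compliance.

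The illustrated size runs from nil (equal rates and outcomes) to a common OR of 0.84 moving to 0.96 (failure 30% v 15%, EVT 70% in both arms). A change from 0.943 to 1.083, across 1, appears with 10-point gaps in both rates. These figures rest on assumed mRS distributions and rates and say nothing about how likely each case is. This rule leaves the primary mITT analysis unaffected.

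**What to change.** In 5.43, delete the wording that makes these two results a violation and a ground for PP exclusion. Replace it with: *Failure to reach mTICI 2b after remedial therapy and re-occlusion at 24 hours are recorded as treatment results and are not in themselves a reason for exclusion from the PP set.*

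Base any PP exclusion on breaches of conduct, such as an eligibility breach at randomisation, or allocated imaging that was not attempted or was replaced by the other arm's imaging. A patient with such a breach stays excluded whatever the reperfusion result. Do not count as breaches the situations that 5.35 itself provides for in the MRI group (FLAIR not obtainable, MRI failed). Those patients followed the protocol, and 5.35 states no matching route for failed perfusion imaging in the control group, so a simple rule of imaging not obtained could again act unequally by arm. The detailed list can be left to the SAP.

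The cost is two sentences in 5.43 and a conduct-based PP definition here or in the SAP. Care is unchanged and no outcome is added. The downside is that the PP set becomes larger and its result may be less favourable than under the present rule.

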### **Termination of endovascular therapy**

- 1)Neurological deterioration suspected to be caused by intracranial hemorrhage;
- 2)Puncture time from the groin was up to 2 hours.
- 3)Spontaneous recanalization of the vessel.
- 4)The same site was embolized up to 5 times.For the procedure, the time of revascularization should be noted in detail;
- 5)the time from imaging to revascularization, the time from onset to revascularization, and the time from admission to revascularization should be calculated and used as baseline information for comparison between the 2 groups.

### **Type of surgical anesthesia**

The surgery is performed by local or general anesthesia.

## **5.5 Postoperative management**

### **5.5.1 Postoperative antiplatelet and anticoagulation therapy**

According to the 2013 and 2018 AHA/ASA guidelines for the early management of acute ischemic stroke [7,8], antiplatelet therapy can be

continued for patients with intraoperative stents, while antiplatelet and anticoagulation therapy should not be initiated within 24 h for patients without intraoperative stents until intracranial hemorrhage has been ruled out by cranial imaging at 24 h postoperatively. Treatment. For non-atrial fibrillation patients, dual antiplatelet therapy (aspirin 100 mg + hydroclopidogrel 75 mg once daily; change to monotherapy after 90 days) and for atrial fibrillation patients, warfarin anticoagulation; the target dose of warfarin is to maintain INR: 2.0-3.0. In addition, newer anticoagulants are available as alternatives to warfarin, including dabigatranate; rivaroxaban; and apixaban. In addition, newer anticoagulants are available as alternatives to warfarin, including dabigatranate; rivaroxaban; and apixaban, selected on an individual basis and applied according to the drug's instructions.

[figure not shown]
### **5.5.2 Blood pressure management**

To prevent overperfusion syndrome, according to the 2013 and 2018 AHA/ASA guidelines for the early management of acute ischemic stroke [7,8], preoperative blood pressure should be controlled below 180/105 mm Hg (1 mm Hg = 0.133 kPa) in revascularized patients, and 20-30 mm Hg below basal blood pressure in hypertensive patients after revascularization, but not below 90/60 mm Hg. When the blood pressure fluctuates abnormally, we should be alert for complications such as intracranial hemorrhage or acute cardiac insufficiency. We recommend that the patient's blood pressure should be measured every 3-5 min during the procedure, and the blood pressure threshold should be sought for the individual patient based on a comprehensive assessment of the patient's cardiac function, vascular condition, and collateral circulation.

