#### **Exclusion criteria:**

1. Active hemorrhage or preexisting tendency to hemorrhage
2. CT shows hypointense areas exceeding 1/3 of the middle cerebral artery supply area, with significant midline structural displacement of cerebral edema
3. Rapid neurological improvement, NIHSS score less than 6, or evidence of spontaneous revascularization
4. Signs and symptoms typical of posterior circulation stroke, such as vertigo, nystagmus, choking, swallowing disorder, ataxia, and gaze to the affected side
5. A stroke attack with epilepsy that prevents an accurate NIHSS score from being obtained.
6. A platelet count of less than  $100 \times 10^9 /L$
7. Hereditary or acquired bleeding tendency, coagulation factor deficiency, recent anticoagulant medication (INR  $>3$  or PPT more than 3 times normal)
8. Presence of signs of cardiac, hepatic or renal failure
9. Baseline blood glucose  $<50\text{mg/dL}$  ( $2.78\text{mmol}$ ) or  $>400\text{mg/dL}$  ( $22.20\text{mmol}$ )
10. Uncontrolled hypertension (SBP  $>185\text{mmHg}$ ; DBP  $>110\text{mmHg}$ )
11. Expected survival less than 90 days.
12. Pregnancy.
13. Chronic obstructive pulmonary disease, inflammation of the lungs, pleural effusion, ARDS, irregular breathing and other pulmonary diseases requiring emergency treatment.
14. Patients with unstable vital signs (heart rate  $\leq 50\text{bpm}$  or  $\geq 120\text{bpm}$ , oxygen

saturation less than  $\leq 90\%$ .  $R \geq 30\text{bpm}$  or  $\leq 10\text{bpm}$ .

15. Patients who are unable to complete the 90-day follow-up

16. A history of severe allergy to contrast media

17. The presence of any other condition that is not suitable for endovascular treatment.

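### Section 5.5.2 contradicts itself on when its 180/105 mm Hg limit applies, and neither reading gives a complete blood-pressure rule

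*Protocol*

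**What the plan says.** Blood pressure appears in two places in the protocol.

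- **Section 5.2.1, exclusion 10.** Patients with uncontrolled hypertension are excluded, with limits of systolic above 185 mm Hg and diastolic above 110 mm Hg. Section 5.42 places this check before randomization: "Confirmation that all enrolled patients meet the inclusion/exclusion criteria".
- **Section 5.5.2.** One sentence carries all the management figures. It opens with its purpose, "To prevent overperfusion syndrome", and cites guidelines. It then says "preoperative blood pressure should be controlled below 180/105 mm Hg" and, after a unit conversion, continues "in revascularized patients, and 20-30 mm Hg below basal blood pressure in hypertensive patients after revascularization, but not below 90/60 mm Hg". The section closes by recommending readings every 3 to 5 minutes during the procedure and a threshold sought for each patient individually.

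Section 5.5.2 belongs to the part headed "5.5 Postoperative management". Its neighbours, 5.5.1 on antithrombotic drugs and 5.5.3 on glucose, both deal with the period after the procedure.

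**The concern.** The limit is labelled for the time before the operation but assigned to patients who, in plain English, have already been revascularized. The stated purpose and the section heading also point to the time after the operation. A site that tries to follow the sentence has to decide for itself which of these markers to believe.

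The stakes are in patient care and in consistency between sites. All haemorrhage and symptomatic intracranial haemorrhage are safety outcomes in section 5.37, and section 5.5.2 itself ties abnormal blood-pressure fluctuation to intracranial haemorrhage. The trial plans 5 to 10 centers, so different readings could produce different care by site. Section 5.1 describes an open-label trial and section 5.32 has the attending physician aware of the allocation. An unclear rule therefore leaves some room for management to differ between groups, although nothing in the protocol shows that it will.

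**Working it through.** The protocol states no statistical figure on this point, so there is none to reproduce. The check sets the passages side by side and follows each reading through.

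**Step 1. Which period do the markers point to?**

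| Marker in 5.5 and 5.5.2 | Period it indicates |
|---|---|
| Label on the 180/105 limit | before the procedure |
| Population (revascularized patients) | after the procedure |
| Purpose (overperfusion) | after the procedure |
| Parent heading and neighbouring sections | after the procedure |
| Closing advice (readings every 3 to 5 minutes) | during the procedure |

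The first marker cannot be squared with the second, and the closing advice does not say which limit or period it modifies.

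**Step 2. Read the limit as preoperative.** The only numeric upper target left after revascularization is 20 to 30 mm Hg below basal, and that is confined to hypertensive patients. Revascularized patients without hypertension then have a floor, if the 90/60 figure is taken to cover them, but no numeric ceiling.

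**Step 3. Read the limit as postoperative.** Hypertensive patients then have two targets at the same time. The protocol does not define basal pressure. Assume, for illustration only, that it is the pressure at entry, and take a systolic value of 180 mm Hg:

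- relative target: 180 − 30 = 150 to 180 − 20 = 160 mm Hg;
- absolute target: below 180 mm Hg.

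A reading of 170 mm Hg meets the absolute target and misses the relative one. The two can be met together, but the text does not say whether meeting the absolute limit is enough.

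**Step 4. Compare with exclusion 10.** The figures differ by 185 − 180 = 5 mm Hg systolic and 110 − 105 = 5 mm Hg diastolic.

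- Under the postoperative reading, the two limits never apply at the same time.
- Under the preoperative reading, a patient at 183/108 passes exclusion 10 and is above the 5.5.2 limit. That patient can be entered and then treated towards the target, so both rules can be satisfied in sequence. What the protocol leaves unsaid is whether puncture waits for this. Section 5.36 sets a target of under 60 minutes from imaging to puncture.

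**The case against.** The strongest reply is that the defect is a single word. Three of the five markers point to the postoperative period, so the label may be a translation slip. Alternatively, revascularized may stand for patients who are to undergo revascularization, which would make the sentence run in order from before to after. Both are plausible, but they lead to opposite readings and the document does not choose between them. Either repair also leaves one of the gaps in steps 2 and 3.

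A second reply is that the section asks for an individual threshold and so never meant one rigid ceiling. It does leave room for clinical judgement, which softens the consequence. It does not settle the period to which 180/105 belongs.

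A third reply is that the rule is the same in both groups, which differ by imaging modality, so no bias in the 90-day mRS comparison has been shown. That is correct, and none is claimed here.

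A reader might go further and infer that exclusion 10 and section 5.5.2 contradict each other, or that sites will admit different patients. The documents do not support either. Exclusion 10 is an entry criterion with a clear time of application and alone governs admission on blood pressure; 180/105 is a treatment target. A reader might also want a count of patients between the two limits. The protocol gives no distribution of entry blood pressure. The planned total of 214 is also the wrong base, since it includes patients who receive drug therapy only.

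**Conclusion.** Section 5.5.2 is wrong as written. Its time label conflicts with the population, the purpose and the heading attached to the same limit, so the rule cannot be followed without guessing. The finding rests on the wording alone and needs no numerical assumption; the basal-pressure example only illustrates how the two targets can part.

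Its reach is the timing of the ceiling for every revascularized patient, a number the protocol does not give. It is an operational safety instruction rather than background text, so it should be corrected. It does not undermine the design or the primary analysis, and it takes no view on which blood-pressure figure is right.

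**What to change.** Reconcile the time label, the population and the section placement of the 180/105 mm Hg limit in section 5.5.2. For each figure in that section (180/105, 20 to 30 mm Hg below basal, and 90/60), state whether it applies before puncture, during the procedure or after revascularization, and to which patients. Where two figures apply to the same patient at the same time, state how they relate, and define basal pressure.

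If 180/105 is meant as a preoperative limit, add how it relates to exclusion 10 and how an eligible patient above it is handled. The entry criterion and the treatment target need not be equal. Which figures apply, and when, is for the clinical investigators to decide.

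The cost is a wording amendment and a note to sites, with no extra patients or procedures.
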